7.2 Analysis Populations

- Intent-to-Treat Population: The intent-to-treat (ITT) population includes all randomized patients. The primary and secondary efficacy analyses will be performed on the ITT population. Patients will be analysed as randomized.
- Per Protocol Population: The per protocol (PP) population includes all patients who have at least one follow-up visit, complete all the treatments as randomized, and have no major protocol deviations. Patients will be analysed as treated.

• Safety Population: The safety population will include all treated patients. The safety population will be analysed for all safety assessments. Patients will be analysed as treated. A summary table of number (%) of patients in each analysis population/set will be provided.

7.3 Demographic and Baseline Characteristics

Descriptive statistics or frequency tabulation will be provided for demographic and baseline characteristics, such as age, gender, race, and ethnicity.

7.4 Effectiveness Analyses

- Primary endpoint

The change from baseline at 4 weeks in TBUT in both study arms will be calculated along with 95% confidence interval. The Paired T-test or Signed rank test for two means (paired observations) (as is appropriate) will be applied for testing the statistical significance of the change within each study group.

Ho: $\mu h - \mu c < 1.5$

HA: $\mu h - \mu c \ge 1.5$

where μ 4w and μ base are the mean at 4 weeks and at baseline, respectively.

- Secondary effectiveness endpoints
- The change from baseline in the TBUT at 4 weeks will be analysed for non-inferiority with a margin of 1.5 using a one-sided two-sample t-test. The non-inferiority hypothesis set will be:

Ho: $\mu h - \mu c > 1.5$

HA: $\mu h - \mu c \leq 1.5$

where μ t and μ c are the mean changes from baseline for Tixel and control, respectively. Thus, the upper limit of the two one-sided 97.5% CI must be < 1.5 in order to demonstrate Tixel non-inferiority.

- The change from baseline at 12 weeks in TBUT will be calculated along with 95% confidence interval. The Paired T-test or Signed rank test for two means (paired observations) (as is appropriate) will be applied for testing the statistical significance of the changes within each study group.
- The change from baseline at 4 weeks and 12 weeks in the Ocular Surface Disease Index (OSDI) will be calculated along with 95% confidence interval. The Paired T-test or

Signed rank test for two means (paired observations) (as is appropriate) will be applied for testing the statistical significance of the changes within each study group.

• The change from baseline at 4 and 12 weeks in the MGS score will be calculated along with 95% confidence interval. The Paired T-test or Signed rank test for two means (paired observations) (as is appropriate) will be applied for testing the statistical significance of the change within each study group.

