4.2 Description of the Study

This study is a randomized, open-label, pilot clinical study comparing the Tixel device to an active control, which will be the LipiFlow System. The goal of this study is to compare between the Tixel device and the LipiFlow System and estimate the magnitude of the differences, if they exist, in terms of safety and effectiveness. A total of up to 30 patients (60 eyes) will be randomized for bilateral treatment and will be assigned in a 1:1 ratio into the Tixel treatment group or the control group at up to 2 study sites in Israel and/or Europe. The evaluator will be masked as to the randomization assignments. Both eyes will receive the same randomized assignment and both eyes of each patient will be evaluated at all time points. One eye will be selected as the designated "study eye" for statistical purposes: The study eye is the eye with the lower baseline TBUT. If both eyes have the same TBUT, the right eye will be the study eye. Outcome Measures

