5.1 Inclusion Criteria

- 1. Age 18 years and older of any gender or race.
- 2. Provision of written informed consent prior to study participation.
- 3. Willingness and ability to return for all study visits.
- A positive history of self-reported dry eye symptoms for three months prior to the study using the Ocular Surface Disease Index (OSDI) questionnaire, and a score of ≥ 23 at the baseline visit.
- Evidence of meibomian gland (MG) obstruction, based on a total Meibomian Gland Score (MGS) of ≤12 in the lower eyelids for each eye. The rater of MGS must not be involved in the study procedure.
- 6. Non-invasive tear break-up time (TBUT) <10 seconds in both eyes. The rater of TBUT must not be involved in the study procedure.
- 7. Agreement/ability to abstain from dry eye/MGD medications for the time between the treatment visit and the final study visit. Ocular lubricants are allowed if no changes are made during the study.
- 8. Fitzpatrick skin type I-VI.

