7 STATISTICAL CONSIDERATIONS

7.1 General Considerations

Descriptive statistics will be used to summarize continuous variables (number of eyes/patients [N], mean, standard deviation (SD) or standard error of the mean, median, maximum, and minimum) and categorical variables (frequency and percentage) at each assessment timepoint. Statistical comparisons within each group will be performed using appropriate statistical methods or models, and the results such as 95% confidence intervals and p values will be reported. All summary tables will be supported with individual patient and eye data listings. Baseline is defined as the last non-missing observation prior to initiation of study intervention. Analyses will be carried out using SAS software or equivalent statistical software.

Further details will be described in the statistical analysis plan, which will be finalized prior to the study database lock.

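### The stated goal is to estimate the differences between Tixel and LipiFlow, but a between-arm analysis is planned for only one of six efficacy outcome-by-visit combinations

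*Combined protocol and SAP*

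**What the plan says.** Section 4.2 sets the aim: "The goal of this study is to compare between the Tixel device and the LipiFlow System and estimate the magnitude of the differences", for both safety and effectiveness. Patients are allocated 1:1. Sections 4.2.1 and 4.2.2 name three efficacy outcomes (TBUT, OSDI, MGS), each at 4 and 12 weeks, which makes six combinations.

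Section 7.4 gives each of the six a change from baseline with a 95% CI and a paired t or signed rank test that "will be applied for testing the statistical significance of the change within each study group" (or near-identical wording). Only one combination also has a comparison between arms. As a secondary analysis, the 4-week TBUT change "will be analysed for non-inferiority with a margin of 1.5 using a one-sided two-sample t-test".

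Section 7.1 states the general rule in the same terms: "Statistical comparisons within each group will be performed using appropriate statistical methods or models". It leaves further detail to a statistical analysis plan to be finalised before database lock, but commits to no between-arm estimate. The sample size in section 7.7 is also built on the within-arm paired test.

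**The concern.** A change inside one arm is not a device effect. It adds together what the device did, non-specific change over time, and regression to the mean. Randomisation lets the contrast between arms cancel whatever is common to both; a paired test inside each arm cannot do that.

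Regression is a live issue because the outcomes also serve as entry limits. Section 5.1 requires for OSDI a positive history "and a score of ≥ 23 at the baseline visit", evidence of gland obstruction "based on a total Meibomian Gland Score (MGS) of ≤12 in the lower eyelids for each eye", and "Non-invasive tear break-up time (TBUT) <10 seconds in both eyes". For TBUT, section 4.2 adds a further selection: "The study eye is the eye with the lower baseline TBUT".

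With only within-arm tests reported, it is natural to set one arm's verdict beside the other's. That comparison can suggest a difference where there is none, or hide a real one, and it does not give the magnitude that section 4.2 asks for.

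**Working it through.** **Tally of section 7.4**

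| Outcome | Visit | Within-arm analysis | Between-arm analysis |
|---|---|---|---|
| TBUT | 4 weeks | yes (primary) | yes (secondary, non-inferiority) |
| TBUT | 12 weeks | yes | none |
| OSDI | 4 weeks | yes | none |
| OSDI | 12 weeks | yes | none |
| MGS | 4 weeks | yes | none |
| MGS | 12 weeks | yes | none |

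The primary hypotheses are printed with symbols that could pass for an arm contrast. The definition beneath them (means at 4 weeks and at baseline) and the paired test show that they are within-arm.

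**Inputs (section 7.7):** n = 15 per arm, mean change 1.5 s, SD of change 1.9 s, paired t-test against zero, two-sided 0.05. These are 4-week TBUT figures. Using them for any other combination is an assumption; the documents give no SD for OSDI, MGS or 12-week TBUT.

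**Step 1: the plan's own figure.** Noncentral t, 14 df, noncentrality (1.5/1.9) × √15 = 3.06. Power is 0.811, in line with the stated 80%.

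**Step 2: equal devices, opposite verdicts.** If both arms have the same true change and each test has power p, exactly one is significant with probability 2p(1 − p).

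| True change in both arms | p | Exactly one arm significant |
|---|---|---|
| 1.0 s | 0.475 | 50% |
| 1.5 s | 0.811 | 31% |
| 2.0 s | 0.966 | 7% |
| 2.5 s | 0.997 | 0.6% |

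**Step 3: different devices, same verdict.** Suppose the true changes are 1.5 and 3.0 s (3.0 is an assumption: 1.5 plus the plan's 1.5 s margin). Both arms are significant with probability 0.8113 × 0.9999 = 0.811.

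**Step 4: what a between-arm interval would deliver.** The half-width is t(0.975, 28 df) × √(2/15) = 2.048 × 0.365 = 0.748 SD of change. At SD 1.9 s this is 1.42 s; over an assumed SD of 1.5 to 2.5 s it is 1.12 to 1.87 s. Power of a two-sided two-sample t-test for a 1.5 s difference is 55% at 15 per arm, and 80% needs 27 per arm.

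**Step 5: what baseline adjustment might add.** The ratio of ANCOVA variance to change-score variance is (1 − r²)/(1 + k² − 2rk), where r is the baseline to follow-up correlation and k is baseline SD divided by follow-up SD. Both ranges are assumptions. For r = 0.3, 0.5, 0.7 the ratio is 0.65, 0.75, 0.85 at k = 1, and 0.85, 0.95, 1.00 at k = 0.7. With arm, baseline and site fitted (26 df), the TBUT half-width is 1.43 s with no gain and 1.15 s at a ratio of 0.65.

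**Step 6: direction of regression, outcome by outcome.**
- OSDI: the limit is read at the baseline visit itself, so regression towards improvement is expected.
- TBUT, lower-eye choice: selecting on the baseline value makes upward regression expected.
- TBUT, entry limit: possible, not certain. Section 5.1 calls the entry measure non-invasive, while Table 1 in section 6.2 measures TBUT with fluorescein strips; error in one need not regress in the other.
- MGS, entry limit: possible, not certain. Section 5.1 does not tie the qualifying value to a visit, and section 7.1 takes baseline as the last value before intervention, so some regression could occur before baseline.

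The size cannot be derived from the documents for any of these.

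**The case against.** The strongest defence has four parts.

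*The objective is not only comparative.* Section 4.1 asks about Tixel's safety and effectiveness, and section 1.3 frames the primary objective as improvement in TBUT. Both fit a within-arm analysis, and section 7.7 sizes for one. This stands as a reason to keep those analyses. It does not remove the comparative goal in section 4.2, which section 1.2 shares.

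*Readers can work out a difference.* A reader might infer that only two p-values will be available for the five combinations. The documents do not support that: section 7.4 plans a 95% CI for each change, and section 7.1 plans N, mean and spread. In the step 3 example the arm intervals would be about 0.45 to 2.55 s and 1.95 to 4.05 s (half-width 2.145 × 1.9/√15 = 1.05 s), which says more than that both arms improved. A crude contrast is derivable. What is missing is a planned one, with its estimator and interval fixed in advance.

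*The illustration belongs to the one combination already covered.* This is correct. A reader might carry the 31% over to OSDI, MGS or 12-week TBUT, but nothing in the documents gives the inputs for that. The figure also falls steeply: near the 1.99 s that section 1.3 quotes for the active arm of another study, it is about 7%.

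*The study is a pilot and detail is deferred.* A pilot meant to estimate differences needs the estimate and its interval. The deferral makes the addition easy, but the text does not promise it.

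**Conclusion.** The gap is real: one of six efficacy combinations has a planned between-arm analysis, and five do not, against a stated goal of estimating the differences. It is a gap in the planned contrasts; no planned within-arm test is invalidated, and the 80% power figure in section 7.7 is correct for the test it describes. The change should be made before the analysis plan is finalised.

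The tally and the reading of section 7.4 need no assumption. The discordance figures (50% to 0.6%) assume independent arms, normal changes and the 4-week TBUT inputs, and are illustrative only.

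Two further inferences go beyond the documents. One is that regression to the mean certainly inflates all three outcomes: it is expected for OSDI and through the lower-eye choice for TBUT, only possible from the MGS and TBUT entry limits, and of unknown size throughout. The other is that the 4-week TBUT comparison is sound as printed. Its symbols do not match their definitions, and requiring an upper limit below 1.5 is doubtful for Tixel minus control when a longer TBUT is better. That must be reconciled as a separate point.

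**What to change.** For TBUT at 12 weeks, and OSDI and MGS at 4 and 12 weeks, pre-specify the Tixel minus LipiFlow difference in change from baseline with a two-sided 95% CI. Use the study eye for TBUT and MGS, and the patient for OSDI. An ANCOVA on arm and baseline value is preferable, with site added if two sites enrol; an unadjusted two-sample difference also closes the gap. Report the same estimate and CI for 4-week TBUT.

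Keep the within-arm analyses, labelled as describing change and not device effect. Present the between-arm results as pilot estimates, and state beside them that:
- there is no sham arm, so a difference near zero fits both devices working or neither;
- the study is open-label for patients, with only the evaluator masked;
- the arms differ in sessions (3 versus 1) and in time from Day 0, because follow-up runs from the last treatment (about week 8 versus week 4, and week 16 versus week 12).

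Cost: analysis-plan wording and a few lines of code, with no new patients or data. ANCOVA uses one or two degrees of freedom, and its gain in precision is uncertain and may be nil. The intervals will be wide (about ±0.75 SD of change; ±1.42 s for TBUT if the SD is 1.9 s), because the trial is powered only for the within-arm test.

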1.3 Primary efficacy endpoint rationale

The primary objective of the study is to determine the efficiency of the therapy, in improving TBUT in eyes with DED due to MGD. This objective was chosen because a reduced TBUT is one of the most common signs of DED due to MGD. TBUT is considered abnormal when shorter than 10 seconds. The reason for choosing the margin of 1.5 second as a success criterion is following the recent IPL study performed by Lumenis and received an FDA approval. In the study the difference between the IPL arm and the control arm was 1.24 second. The IPL arm was 1.99 second in combination with MGX, and the sham +MGX was 0.75 meaning that the IPL alone was responsible to 1.24 second from baseline to 4 weeks follow-up (Effectiveness of Intense Pulsed Light for Improving Dry Eye Syndrome - Study Results - ClinicalTrials.gov).

Novoxel

Synopsis -Clinical Protocol Number: CLN 0798 Rev. 002

June 21, 2021

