7.7 Sample Size Justification

15 patients will be enrolled in each treatment group.

Sample size rationale:

The sample size calculation was based on an expected change from baseline at 4 weeks in TBUT score of 1.5 seconds with a standard deviation of 1.9 seconds within each study group.

Sample size justification:

A sample size of 15 will have 80% power to detect a difference in means of 1.5 assuming a standard deviation of differences of 1.9 (effect size of 0.78), using a paired t-test with a 0.05 two-sided significance level.

Reference:

7.8 **Poolability Analysis**

Patient demographic characteristics and background variables shall be summarized. To ensure poolability in case of more than one site, primary effectiveness will be analysed by site.

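### The primary TBUT test has no concurrent comparator and is powered only against zero, while its printed hypotheses put the null at 1.5 s; a significant result would show a change from baseline, not a device effect

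*Combined protocol and SAP*

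**What the plan says.** - **Worded primary test (7.4).** The 4-week TBUT change is calculated in both arms with a 95% CI. A paired t-test or signed rank test "will be applied for testing the statistical significance of the change within each study group".
- **Printed primary hypotheses (7.4, directly below).** The null reads "Ho: $\mu h - \mu c < 1.5", with the alternative at 1.5 or more. The explanatory line defines different symbols, which "are the mean at 4 weeks and at baseline, respectively".
- **Sample size (7.7).** "15 patients will be enrolled in each treatment group". The planning assumption reads: "expected change from baseline at 4 weeks in TBUT score of 1.5 seconds with a standard deviation of 1.9 seconds within each study group". The claim is that "A sample size of 15 will have 80% power to detect a difference in means of 1.5", using a paired t-test at two-sided 0.05.
- **Rationale (1.3).** The section introduces its reasoning with "The reason for choosing the margin of 1.5 second as a success criterion". It then cites a study of another device in which the active arm gained 1.99 s and "the sham +MGX was 0.75 meaning that the IPL alone was responsible to 1.24 second from baseline to 4 weeks follow-up".
- **Comparator (4.2 and 7.4).** The control is LipiFlow, an active device, and the study is described as a pilot. The only between-arm TBUT analysis is a secondary non-inferiority test.

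**The concern.** Section 1.3 removes the control-arm change before crediting the cited device: 1.99 − 0.75 = 1.24 s. The worded primary analysis in 7.4 has no corresponding step. It tests the raw change in each arm, so whatever would have happened without the device stays in the estimate.

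This design gives reasons to expect some such change. Entry requires a low TBUT (5.1), the study eye is the one with the lower baseline TBUT (4.2), and the selecting measurement can serve as baseline (7.1). Regression to the mean would then raise the follow-up values even with no treatment effect.

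The objective in 1.3 is whether the therapy improves TBUT, and a significant within-arm p-value cannot answer that alone. The plan also gives the primary test two incompatible nulls, zero and 1.5 s, so the criterion the result will be judged by is not fixed.

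**Working it through.** **Inputs.** n = 15 per arm, planned change 1.5 s, SD of change 1.9 s, two-sided α = 0.05 (all 7.7); external control-arm change 0.75 s (1.3); printed null 1.5 s (7.4).

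**1. Reproduce the stated power.** One-sample (paired) t-test, df = 14, critical value 2.145, noncentrality = (δ/SD)·√n.
- Null at zero: (1.5/1.9)·√15 = 3.06, power 81.1%. With the rounded effect size of 0.78 in 7.7, power is 80.2%.
- The stated 80% is therefore reproduced, and the null it implies is zero.

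**2. Chance of a significant gain if the true change has no device component.** Same test, null at zero, upper tail only.

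| True change (s) | Noncentrality | P(significant gain) |
|---|---|---|
| 0 | 0 | 2.5% |
| 0.25 | 0.51 | 6.9% |
| 0.5 | 1.02 | 15.6% |
| 0.75 | 1.53 | 29.6% |

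Counting both tails at 0.75 s gives 29.7%. The signed rank test gives about 27% (5,000 simulated trials, normal data). With assumed values not in the documents, the 0.75 s figure is 43.8% at SD 1.5, 21.8% at SD 2.3, and 25.9% with 13 evaluable patients at SD 1.9.

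**3. The same test against the printed null of 1.5 s.** Noncentrality = ((μ − 1.5)/1.9)·√15.

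| True change (s) | One-sided α 0.025 | One-sided α 0.05 |
|---|---|---|
| 0.75 | 0.03% | 0.1% |
| 1.5 (planned) | 2.5% | 5% |
| 3.0 | 81.1% | 89.6% |

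At the planned change the truth lies on the null boundary, so power equals α. Reaching 81% at one-sided 0.025 needs a true change of 3.0 s, twice the planned value. The sample size fits the zero null and not the printed one.

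**4. Precision of the randomised comparison.** SE of the Tixel-minus-LipiFlow difference = 1.9·√(2/15) = 0.694 s. With df = 28 the 95% CI half-width is 2.048 × 0.694 = 1.42 s.

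**The case against.** The strongest case against the point has four parts.

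- **The plan does not test only against zero.** Section 7.4 prints a 1.5 s null and 1.3 calls 1.5 s a success criterion. That is twice the 0.75 s control-arm change, and on that reading a true 0.75 s would almost never succeed (0.03% to 0.1%). This stands, so the 30% depends on the zero-null reading. It does not rescue the plan, because the printed null contradicts the worded test and leaves the stated sample size with 2.5% to 5% power. A 1.5 s null within one arm would still have no comparator.
- **No decision rule is stated.** A reader might infer that a device no better than the cited control would be declared effective in about 30% of trials. The documents do not support that. Nowhere do they equate a significant within-arm p-value with effectiveness, and 4.2 describes a pilot meant to compare the devices and estimate differences. What can be said is that the result would be statistically significant.
- **The 0.75 s is not this trial's non-device change.** It comes from another study's sham-plus-MGX arm, with no n, SD or standard error given. It includes gland expression and is best read as the upper end of a range. Nor can half of the expected 1.5 s be assigned to non-device change on this evidence.
- **A between-arm analysis already exists.** It is secondary and framed as non-inferiority to an active device. Its printed direction (upper limit of Tixel minus control below 1.5, where larger values are better) is a separate problem, so it does not supply the missing comparison as written.

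**Conclusion.** The point holds in two parts.

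First, the worded primary analysis has no concurrent comparator and the sample size works only against zero. A significant result would establish a rise in TBUT from baseline and nothing about its cause. As an upper-end illustration, a rise of 0.75 s with no device component would be significant in about 30% of trials, falling to 16% at 0.5 s and 7% at 0.25 s. This rests on n = 15, SD 1.9, two-sided 0.05, normal changes and the zero null.

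Second, the primary null is stated in two ways that cannot both apply. This is a contradiction in the text and depends on no borrowed figure. Under the printed 1.5 s null, power at the planned effect is 2.5% to 5%, against the stated 80%.

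The evidence does not support a fixed false-success rate of 30% or the use of 0.75 s as a hurdle. A lower confidence limit above an external point estimate of unknown precision, from an arm given a different treatment, would not prove a device effect.

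**What to change.** **In 7.4:**
- State one primary null, zero or 1.5 s, and make the symbols match their definitions. If 1.5 s is kept as the null, 7.7 must be recalculated.
- State that a significant within-arm result is a change from baseline and is not by itself attributable to the device.
- Report the randomised Tixel-minus-LipiFlow difference in 4-week TBUT change, with its 95% CI, as the comparative result. It removes only the non-device change common to both arms. Because 6.4 times the visit from the last treatment, it falls about 8 weeks after Day 0 for Tixel and 4 weeks for LipiFlow; the report should say so.

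**In 7.7:** state that the 80% is power against a null of zero, and give the expected half-width of the between-arm interval (about 1.4 s at SD 1.9).

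The 0.75 s may be shown as context if labelled as external, from a sham-plus-MGX arm, but not as a pass/fail threshold.

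**Cost:** wording and one further interval, with no added patients or visits, if the zero null is chosen. The real price is a less favourable claim, and a comparative interval wide enough to show how little 15 patients per arm can settle.

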7.9 Safety Analyses

The incidence rate of device-related adverse events will be calculated along with 95% CI. The reporting period is from baseline through the last study visit.

Secondary safety endpoint:

- The evaluation of discomfort and pain will be summarized in appropriate tables by visit.
- Changes from baseline in ocular surface staining, and intraocular pressure will be calculated along with 95% CI by study group and visit. The Paired T-test or Signed rank test for two means (paired observations) (as is appropriate) will be applied for testing the statistical significance of the changes within the study group.
- Cornea OCT evaluation to detect changes (cornea thickness, cornea deamination) following treatment. Changes in Cornea OCT evaluation will be summarized in descriptive tables for the Tixel group.

Adverse events will be coded using the Medical Dictionary for Regulatory Activities (MedDRA, most updated version) terminology and presented in tables by System Organ Class (SOC) and Preferred Term (PT).

AE data will be listed individually and summarized by SOC and by PT within a system organ class.

Treatment-emergent adverse events (TEAEs) are those with onset after initiation of study intervention or if occurring prior to initiation of study intervention, worsened after initiation of study intervention. Only treatment-emergent events will be summarized. All events in the clinical database regardless of when they occurred will be provided in a data listing. Definitions of adverse events, serious adverse events, and categorizations of events can be found in Appendix D.

An overall summary will be presented which gives the number and percentage of patients that experienced any TEAE (overall, ocular, and non-ocular), experienced any treatment related TEAE (overall, ocular, and non-ocular), permanently discontinued treatment due to a TEAE (overall, ocular, and non-ocular), interrupted treatment due to a TEAE (overall, ocular, and non-ocular), experienced a treatment emergent serious TEAEs (overall, ocular, and non-ocular), and that died.

A listing of serious TEAEs will be provided. Continuous safety endpoints shall be summarized using summary statistics such as means, medians, standard deviations, minima, maxima, and relevant percentiles.

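### Sections 7.4, 1.3 and 7.7 give 1.5 s three different roles for the primary endpoint, so the printed hypotheses and the 80% power cannot both stand

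*Combined protocol and SAP*

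**What the plan says.** Three sections of the combined protocol and SAP use 1.5 s for the primary endpoint.

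- **Section 7.4, printed hypotheses.** The null is "Ho: $\mu h - \mu c < 1.5" and the alternative is "HA: $\mu h - \mu c \ge 1.5". The line below them explains different symbols: the second of the two means it defines is labelled "base are the mean at 4 weeks and at baseline, respectively". Taken with that line, the hypotheses concern the change within an arm, and 1.5 s is the boundary of the null.
- **Section 7.4, prose.** A paired t-test or signed rank test "will be applied for testing the statistical significance of the change within each study group". It mentions no 1.5 s offset.
- **Section 1.3.** Under a heading about the primary endpoint it gives "The reason for choosing the margin of 1.5 second as a success criterion" and refers to an earlier IPL trial: 1.99 s in the IPL arm, 0.75 s in the sham arm, a difference of 1.24 s.
- **Section 7.7.** The calculation is "based on an expected change from baseline at 4 weeks in TBUT score of 1.5 seconds", with an SD of 1.9 s. It concludes: "A sample size of 15 will have 80% power to detect a difference in means of 1.5", using a two-sided paired t-test at 0.05.

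The secondary endpoints in 7.4 (TBUT at 12 weeks, OSDI, MGS) use the same paired-test wording with no 1.5 s boundary. So do the staining and pressure changes in 7.9: the test "will be applied for testing the statistical significance of the changes within the study group".

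**The concern.** One number cannot be both the value that the trial must show it exceeds and the value that it expects to observe. If the true change sits on the null boundary, power equals the significance level whatever the sample size. The 80% in 7.7 therefore belongs to a different test from the one that the hypotheses in 7.4 describe.

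The effect is on the primary claim. Someone who follows the prose and 7.7 needs the confidence interval for the change to exclude zero. Someone who follows the printed hypotheses needs it to exclude 1.5 s. Section 1.3 permits a third reading, a threshold on the observed mean. If the choice is left until the data are seen, the success rule becomes post hoc.

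**Working it through.** **Inputs.** n = 15 per arm, expected change 1.5 s, SD of differences 1.9 s, two-sided 0.05, printed effect size 0.78 (all 7.7); null boundary 1.5 s (7.4); 1.99 s, the IPL-arm change cited in 1.3. I use 1.99 s only as an assumed scenario: it comes from another device combined with MGX. A true change of 2.5 s is a further assumption. No dropout allowance is applied, since 7.7 gives none.

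**Formula.** The one-sample (paired) t-test has 14 degrees of freedom and noncentrality (true change − null value) / 1.9 × √15. Power is the noncentral-t probability beyond the critical value. The standard error is 1.9/√15 = 0.491 s.

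**Step 1: reproduce 7.7 (null of zero).** The effect size is 1.5/1.9 = 0.789 and the noncentrality is 0.789 × √15 = 3.06. Two-sided power at 0.05 is 81.1%, or 80.2% with the printed 0.78. The stated 80% is correct as power against zero.

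**Step 2: use the printed null of 1.5 s.** At a true change of 1.5 s the noncentrality is (1.5 − 1.5)/1.9 × √15 = 0, so power equals alpha. The document gives no sidedness for these hypotheses, so both usual levels are shown.

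| True change | Null 0, two-sided 0.05 | Null 1.5, one-sided 0.05 | Null 1.5, one-sided 0.025 |
|---|---|---|---|
| 1.5 s (7.7) | 81% | 5.0% | 2.5% |
| 1.99 s (assumed) | 96% | 24% | 15% |

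At the assumed 2.5 s, power against 1.5 s is 62% or 48%. To reach 80% against 1.5 s with 15 patients, the true change must be about 2.78 s (one-sided 0.05) or 2.98 s (one-sided 0.025).

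**Step 3: observed mean needed, if the sample SD is 1.9 s.**
- Against zero: 2.145 × 0.491 = 1.05 s.
- Against 1.5 s, one-sided 0.05: 1.5 + 1.761 × 0.491 = 2.36 s.
- Against 1.5 s, one-sided 0.025: 1.5 + 2.145 × 0.491 = 2.55 s.

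The range in which the two rules disagree contains both the planned 1.5 s and the cited 1.99 s.

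**Step 4: how often the rules disagree.** In practice, an arm that rejects 1.5 s also rejects zero, so the disagreement is the difference in power. At a true 1.5 s: 81.1% − 5.0% = 76%, or 81.1% − 2.5% = 79%. At a true 1.99 s it is 72% or 81%. Simulation agrees to within half a percentage point.

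**Step 5: the third reading.** Suppose success meant an observed mean of at least 1.5 s plus significance against zero. The chance is then about 50% at a true 1.5 s and 84% at a true 1.99 s. The document does not state this rule. It is shown because the words in 1.3 would allow it.

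**Step 6: size needed for 80% power against 1.5 s.** At a true 1.99 s the excess over the null is 0.49 s. The normal approximation is (1.9/0.49)² × (1.645 + 0.842)² ≈ 93, or (1.9/0.49)² × (1.960 + 0.842)² ≈ 118. The exact t calculation gives 95 or 120 per arm. At the assumed 2.5 s it gives 24 or 31.

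**The case against.** The strongest reply is that the operative test is clear and the two formula lines are a slip. The prose in 7.4, the calculation in 7.7 and the parallel wording for every other paired comparison all fit a test against zero. The printed lines put equality in the alternative, which is not standard, and come with no one-sided level. Their letters do not match the definitions beneath them and recur in the non-inferiority block, so a copying or rendering fault is plausible. I accept this as the likeliest explanation. It does not dispose of section 1.3, which separately calls 1.5 s a success criterion for the primary endpoint.

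Section 1.3 is itself ambiguous: it says margin and argues from a between-arm difference, which would suit the non-inferiority comparison better. That is a further reason to state the role of 1.5 s, because the heading ties it to the primary endpoint.

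It is also fair to say that 2.5% to 5% is simply alpha, as it would be at any sample size. The figure shows that two sections are incompatible. It does not show that the trial is under-powered for a test against zero.

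Finally, the study is a pilot, 95% confidence intervals are reported on either reading, and 7.1 leaves further details to a SAP finalised before database lock. These points limit the harm. But an interval does not say whether its lower limit must clear 0 or 1.5 s, and a SAP that copied 7.4 would inherit the conflict.

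**Conclusion.** The inconsistency is real and must be fixed. The primary success rule has at least two incompatible readings, and nothing in the document ranks them. The 80% power is sound for a test against zero. It cannot be claimed for the hypotheses as printed, under which the planned effect would succeed in only 2.5% to 5% of arms. At that planned effect the two readings give opposite conclusions in about 76% to 79% of cases per arm.

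These figures rest on n = 15, an SD of 1.9 s and normally distributed changes. The low power is conditional on the printed lines governing, which is probably not what the sponsor intended. The spread within each range reflects the unstated sidedness. Confidence in the conflict itself is high.

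**What to change.** **Preferred: wording only, before database lock.**
- In 7.4, write the primary hypotheses for each arm as H0: μ_4w − μ_base = 0 against a two-sided alternative of not equal to 0, at 0.05. Use the same symbols in the hypotheses and in their definitions.
- Keep 1.5 s in 7.7 as the planning effect, and keep reporting the 95% confidence interval.
- In 1.3, state the single role of 1.5 s for the primary endpoint: either a planning value or a descriptive threshold on the observed mean. Separate this from its use as the non-inferiority margin.

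This adds no patients and leaves the 80% statement valid.

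**If the sponsor does intend 1.5 s as the null boundary,** the 80% claim in 7.7 must be withdrawn. There are then two options:
- Keep 15 per arm and state the power against 1.5 s, with its sidedness and an assumed true change above 1.5 s. At an assumed 1.99 s that is 24% or 15%.
- Re-size for 80% power: 95 to 120 per arm at an assumed 1.99 s, or 24 to 31 at an assumed 2.5 s.
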